The important complication rate will be calculated at 6 month intervals for both groups; as a guideline, the protocol committee considers that a true difference of more than 15 percentage points in the complication rates for the three surgical procedures to represent an important difference between groups. Stopping the study will be considered by the DSMB during regularly scheduled reviews if they find compelling evidence of an important difference based on point and interval estimates of the important complication rates in the three study arms. While the true difference of 15 percentage points or greater can guide the DSMB considerations, final decisions about a magnitude of difference in safety risk that warrants a recommendation to stop the study lie fully within the discretion of the DSMB.

N.5. Adverse Events

Adverse event means any untoward medical occurrence associated with a clinical study in humans, whether or not considered study-related. An adverse event (also referred to as an adverse experience) can be any unfavorable and unintended sign (e.g. an abnormal laboratory finding), symptom, or disease temporally associated with study intervention, and does not imply any judgment about causality. Lack of efficacy does not meet adverse event criteria.

Reporting of Adverse Events

Adverse events that occur during the study period (from the time of treatment initiation through the completion of follow-up) will be recorded on designated case report forms. Failure of the study interventions to adequately treat prolapse (failure of efficacy) will be captured by the study endpoints and will not be recorded as an adverse event.

The degree of information collected will vary with follow-up time to minimize participant burden over this period, while ensuring that AE data collected are adequate to allow comparison of the AE risk associated among treatments. The decisions about whether or not to collect an adverse event are based in part on the relationship of the event to the pelvis or to surgery (note that this relationship is different than the relationship to the study intervention).

Guidelines:

- 1. During the first six weeks following surgery: All AEs and SAEs of grade II or higher will be captured for the first six weeks following surgery.

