5. STUDY DESIGN

5.1. Description of study design:

PPAR is designed to fill several gaps regarding the patient perspective and to determine which postoperative events are associated with a negative impact on decision-making and quality of life outcomes, or in other words resulting in harm. This is outlined in Figure 1.

PPAR is designed to provide supplementary information to the ASPIRe core study. ASPIRe is a three-armed surgical trial comparing transvaginal mesh (Uphold LITE) vs. sacral-colpopexy, and native tissue repair vs. sacral-colpopexy and transvaginal mesh for post-hysterectomy vaginal vault prolapse. In the ASPIRe protocol, AEs will be assessed longitudinally through the 5 year trial duration and routinely at 6 month intervals.

Standard AE Capture Process

ASPIRe AEs are captured by research staff either by phone or in-person follow-up visits. Collection includes both active (select AEs that patients are questioned about specifically) and passive capture (rely on patient reporting to staff that AE occurred). AEs are then logged into an AE log form, for which there are 7 fields that are required (Table 12). The routine process is for research staff to collect any additional documentation of the event, and then to complete the AE Log form and the 7 additional fields with input from each site's investigators. This process is primarily designed to meet several regulatory guidelines on AE reporting. This process will be referred to as "Usual Ranking" of AEs.

Table 12. Standard AE Descriptors Collected in Usual Ranking (AE Log Form)

AE Descriptor:	Response Options:
Grade	Mild, moderate, severe, life-threatening, death
Attribution: Relation to Study Intervention	Unrelated, unlikely, possible, probable, definite
Action	None, sought medical attention, additional surgery, hospitalization, other, unknown
Outcome	Resolved, resolved w/sequelae, unresolved, fatal, unknown
Expected AE?	Yes or no
Serious AE	Yes or no
Continuing?	Yes or no

PPAR AE Capture Process

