For PPAR, we will obtain patient input on pre-selected adverse events and symptoms through "active capture". The team recognized the main limitation of the active capture approach is that there may be AEs that patients consider important that may not be included in PPAR. However, we believe that for this supplementary study, active capture would be the most feasible approach to collecting data that is reliable. We believe this data will be meaningful and will allow us to begin the process of assessing the impact of AEs from the patient perspective.

We anticipate there will be adverse events that are discrete events (e.g. urinary tract infection) and others that are adverse symptoms (e.g. dyspareunia). For discrete adverse events, we will ask patients to grade the severity and rate the impact of the event. For adverse symptoms, patients will be asked to provide information about severity, frequency, and impact of the adverse symptom. This participant assessment will be referred to as "Patient Ranking" of AEs and is presented in Table 13.

Table 13. PPAR Adverse Event and Symptom Attributes

AE Descriptor:	Patient Question*	Response Options:
1. Adverse events		
Severity at its worse	How would you grade or rank this event?	Mild, moderate, severe, life-threatening
Impact	How much did the event/ symptom interfere with your usual or daily activities?	Not at all / A little bit / Somewhat / Quite a bit / Very much
2. Adverse symptoms		
Frequency	How often did you experience the symptom	Rarely, occasionally, frequently, almost constantly
Severity at worst	What was the severity level of the symptom at its worst?	Mild, moderate, severe, very severe
Impact	How much did the event/ symptom interfere with your usual or daily activities?	Not at all / A little bit / Somewhat / Quite a bit / Very much

5.2. Rationale for AEs/symptoms included in PPAR:

For the standard AE capture process in ASPIRe, AE capture will follow these guidelines:

- 0-6 weeks postop: All AEs grade 2 (moderate) or higher are captured.
- 6 weeks to 6 months: All AEs and SAEs involving death, hospitalization or ER visit, and grade 2 or higher at least possibly related to surgery in the opinion of the investigator are captured.
- After 6 months: Deaths, AEs and SAEs grade 2 or higher that are at least possibly related to pelvis or surgery in the opinion of the investigator are captured.

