7. DESCRIPTION OF STUDY INTERVENTIONS

The PPAR AE Log form will be similar to the Standard AE Log Form used for the usual ranking process to capture the PPAR attributes (grade/severity at its worst, impact, frequency). The 6-week and 6-60 month postoperative ASPIRe visit forms will include the PPAR inventory items under "Subject Reported Complications Table" to streamline capture from the coordinator standpoint. PPAR items on these forms will be highlighted using a mechanism such as an *asterisk to alert the coordinator that additional PPAR forms will be required for those AEs/symptoms.

We will collect PPAR data at the time points outlined in Table 14.

Table 14. Collection of Patient-Perspective Information for AEs

Time point	Rationale
Initial identification of AE	Provides patient's initial perspective *This gets updated at each interaction such that the "most severe" reporting by the patient gets recorded.
12 months postop	Provides information about whether her perspective changed over time
3 years postop (or final visit)	Provides her final perspective about the AE at the primary endpoint of the ASPIRe trial

When a PPAR AE/symptom is identified, the research staff will capture the PPAR AE/symptom attributes with the patient. The research staff will complete the usual process as needed to complete the Standard AE Log Form as well as the PPAR AE log Form. The investigators will be masked to the patient reporting and the patients will be masked to the investigator reporting. The attributes will be captured in an ongoing fashion such that the highest severity reported by the participant will be recorded on the PPAR AE log. Her perspective will be reassessed at 12 months and 3 years postoperative. Whether or not (and when) the AE/symptom has resolved will be determined based on the Standard ASPIRe AE log form by the field "Event End Date".

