8. STATISTICAL CONSIDERATIONS AND ANALYTICAL PLAN

8.1. Sample size:

There is very little information regarding patient perspective for AEs.

Table 15 presents information regarding AEs in previous PFDN trials that have included pelvic organ prolapse repair, specifically apical suspension procedures.

Table 15. AEs in Prior PFDN Trials Including Surgical Treatment for Apical Prolapse

PFDN Trial	Total Number of Patients in Trial	Number of SAEs	Number of AEs Possibly Related to Study	Unexpected AEs	Total AEs
SUPeR	184	18 AEs	~60% of total AEs		300 AEs
OPUS	337	52*	219 AEs	31*	302 AEs

PFDN Trial	Total Number of Patients in Trial	Number of SAEs	Number of AEs Possibly Related to Study	Unexpected AEs	Total AEs
OPTIMAL	374	84 SAEs (but only 14 likely related to study)	160 patients		? 244 patients
ASPIRe	363				

^{*}Includes events likely unrelated to study (e.g. colon cancer, knee fracture, goiter)

An analysis of the SUPeR data available at the time of protocol development indicated that approximately 300 AEs had been reported, with slightly more than 60% having a relationship of possibly related or greater to the intervention. Approximately 50% of women had reached the 1-year follow-up for SUPeR at that time. Based on this information, we estimated that 400 AEs would be identified for ASPIRe that would be possibly related to the study, including all grades. Assuming that the distribution of severity is comparable to that found in the SUPeR trial, this study is powered to provide an interval estimated for the agreement between clinician grading of +/- 0.11. That is, if the study estimate of Kappa measuring the agreement is 0.5, we will be 95% confident that the true agreement is in the range of 0.39 to 0.61.

8.2. Statistical methods:

Aim 1: To compare patient vs. routine rankings of AE/symptom grade.

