We will compare the proportions of AE rankings based on grade using Chi-square between patient and usual rankings. We will also determine the inter-rater agreement between the two groups by estimating the Cohen's Kappa coefficient. In addition to these tests, which provide an overall assessment of whether or not the ratings between clinicians and patients agree or disagree, we will also use extensions of generalized linear models that are appropriate for the ordinal nature of these outcomes and the paired structure of the patient/clinician ratings to evaluate how patients and clinicians disagree should the initial tests suggest differences. Specifically, we will explore classes of events for which the rankings of patients are consistently lower or higher than those of the clinicians.

Aim 2: To estimate the association between patient rankings of AE/symptom grade to Decision Regret and Decision Satisfaction in ASPIRe.

We will estimate the association between patient determined grade and impact of AEs and Decision Regret and Decision Satisfaction scores using linear model approaches. Mean scores for these scales will be compared between women who experienced serious AEs and different grades and impact of AEs. These scores will be compared at the 12 month and 3 year time points.

Aim 3: To estimate the association between AEs/symptoms and patient and quality of life and patient global impression outcomes (SF-12 and PGI-I).

We will utilize a combination graphical summaries and linear model-based approaches to compare the mean SF-12 and PGI-I scores between women who experienced severe AEs/symptoms and to compare these means across women who exhibit the different AE/symptom grades. These scores will be compared at the 12 month and 3 year time points.

Aim 4: To determine if patient perspective about AEs/symptoms changes over time.

We will determine the intra-observer agreement for patient rankings of AE/symptom grade and impact over time using weighted Kappa measures. We will also explore whether the impact of specific events plateaus over time, taking into account her perception of if and when the AE/symptom resolved.

Aim 5: To compare AE/symptom severity ranking between patient rankings and the Pelvic Floor Complication Scale.

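### PPAR Aim 1 pairs patient and clinician grades, but the standard log takes only clinician grade 2 or higher while the sample size counts all grades; if the floor applies to the pairs, the comparison is biased

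*Protocol*

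**What the plan says.** Appendix B section 4 defines the routine ranking in Aim 1 as the network's usual AE grading process. Section 5.1 places that grade on the standard AE log, where Table 12 offers "Mild, moderate, severe, life-threatening, death". The patient scales in Table 13 also start at mild.

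Section 5.2 gives the standard capture rule in three periods:
- First six weeks: "0-6 weeks postop: All AEs grade 2 (moderate) or higher are captured".
- Six weeks to six months: "All AEs and SAEs involving death, hospitalization or ER visit, and grade 2 or higher at least possibly related to surgery".
- After six months: "Deaths, AEs and SAEs grade 2 or higher that are at least possibly related to pelvis or surgery".

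Main protocol section N.5 has the same floor ("All AEs and SAEs of grade II or higher will be captured for the first six weeks following surgery"), and the reportable AE definition in SAP section 10.2 repeats it.

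For PPAR items, section 7 says "The research staff will complete the usual process as needed to complete the Standard AE Log Form", together with the PPAR log. It does not say whether an item the clinician considers mild receives a clinician grade.

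Section 8.1 plans on a different base: "we estimated that 400 AEs would be identified for ASPIRe that would be possibly related to the study, including all grades". From this it derives a 95% interval of 0.39 to 0.61 around a kappa of 0.5. For the direction of disagreement, section 8.2 adds that "we will explore classes of events for which the rankings of patients are consistently lower or higher than those of the clinicians".

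**The concern.** Agreement between two raters can be estimated without selection bias only if entry to the sample does not depend on one rater's score. Under the capture rule it would depend on the clinician's. An event the clinician calls mild and the patient calls severe could drop out, while an event the clinician calls moderate and the patient calls mild would stay.

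Both Aim 1 results are exposed: the kappa and the account of where patients rank lower or higher. The background in Appendix B section 3.2 says clinicians under-report symptom severity relative to patients, so the pairs at risk are the ones that bear on that statement. The planned precision would also rest on more pairs than the rule delivers. The trial's primary efficacy and safety analyses are not affected.

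**Working it through.** **1. The plan's own figure.** The simple large-sample half-width for kappa is 1.96 x sqrt[po(1-po) / (n(1-pe)^2)], where pe is chance agreement and po = pe + 0.5(1-pe) when kappa is 0.5. With n = 400:
- pe 0.30 gives 0.067.
- pe 0.50 gives 0.085.
- pe 0.67 gives po = 0.835 and half-width 0.110.
- pe 0.75 gives 0.130.

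The stated +/-0.11 is therefore attainable with 400 pairs if chance agreement is about 0.67. It cannot be confirmed, because the SUPeR severity distribution is not given.

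**2. Number of pairs.** If a share m of the 400 events is clinician-mild and unlogged, 400(1-m) pairs remain: 320, 280 and 200 for m = 20%, 30% and 50%. With kappa and pe held at their planning values, the half-width scales with the square root of 400/n:
- 0.110 x sqrt(400/320) = 0.123
- 0.110 x sqrt(400/280) = 0.131
- 0.110 x sqrt(400/200) = 0.156

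**3. Direction.** When the clinician grades mild, the patient cannot grade lower. Truncation therefore removes no patient-lower pair, and the patient-lower share becomes P(lower)/(1-m) whatever the grade distributions. All the disagreement that is lost is of the patient-higher kind.

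**4. Kappa with no true difference between raters.** Assumptions: four grades, latent bivariate normal severity, identical patient and clinician distributions, and correlation set so that the all-grade kappa is 0.50. The clinician-mild row is then deleted.

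Worked case with distribution .50/.35/.12/.03:
- pe = .2500 + .1225 + .0144 + .0009 = 0.388, and po = 0.388 + 0.5 x 0.612 = 0.694. Disagreement is 0.306, or 0.153 in each direction.
- After deletion, patient-lower is 0.153/0.50 = 0.306. Patient-higher is 0.124 and agreement is 0.570.
- Chance agreement is now 0.427, so kappa = (0.570 - 0.427)/(1 - 0.427) = 0.25.

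Kappa after truncation, by mild share and by the moderate/severe/top split of the remaining events:

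| Mild share | 60/30/10 | 70/25/5 | 80/15/5 |
|---|---|---|---|
| 20% | 0.42 | 0.40 | 0.36 |
| 30% | 0.37 | 0.35 | 0.30 |
| 50% | 0.27 | 0.25 | 0.20 |

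At 50% mild, the patient-lower share rises from 0.15-0.16 to 0.29-0.32. Steeper distributions give lower values: .20/.70/.08/.02 gives 0.30. With 10% mild and 80% moderate, where chance agreement is 0.66 and so close to what +/-0.11 implies, kappa falls to 0.38.

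**5. Kappa when patients truly grade higher.** Clinician distribution .50/.35/.12/.03, latent correlation 0.7:

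| Patient distribution | Kappa, all to retained | Mean patient-minus-clinician grade | Retained: patient higher v lower |
|---|---|---|---|
| .30/.40/.24/.06 | 0.26 to 0.17 | +0.38 to +0.17 | 33% v 18% |
| .10/.40/.40/.10 | 0.07 to 0.12 | +0.82 to +0.57 | 55% v 5% |

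The excess shrinks but keeps its sign. In the second row unweighted kappa rises.

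**The case against.** The strongest reply is that truncation of the PPAR pairs is inferred, not stated. Section 5.2 attaches the floor to the standard ASPIRe process. Section 7 triggers PPAR capture when an item is identified and calls for both logs. Table 12 offers mild, Appendix B-3 defines dyspareunia by its presence rather than by a grade, and section 8.1 counts all grades. SAP section 3.2 also gives PPAR its own analysis plan, which may settle the pairing. All of this stands, so a reader who concludes that the pairs are certainly truncated goes further than the documents do.

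It does not close the point. Section 7 invokes the usual process only as needed, and no PPAR exemption from the floor appears. The SAP's complication-table entries are coded as AE, SAE or not evident, without a grade for each item, so the documents show no other source for the clinician grade.

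Two stronger inferences are tempting. One is that truncation always depresses kappa. It does so in every equal-distribution case tried, but kappa can rise when patients grade much higher, or when disagreement lies almost only among clinician-mild events (0.57 to 0.83 in one constructed table). The other is that it makes patients look milder than clinicians. That follows when the raters truly agree on average. If patients grade higher, as the background expects, the usual effect is attenuation. Recording the patient's highest reported severity (section 7) also pushes patient grades up. The Aim 1 hypothesis itself is non-directional.

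**Conclusion.** The firm finding is an unreconciled conflict: a capture rule that starts at clinician grade 2 against a precision statement based on all grades. The bias is conditional on the floor being applied to PPAR pairs. In that case, with equal distributions and a true kappa of 0.50, kappa is understated by about 0.08-0.14 at 20% mild, 0.13-0.20 at 30% and 0.23-0.30 at 50%. From 30% upward this exceeds the planned half-width of 0.11. The patient-lower share is inflated by a factor of 1/(1-m).

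These sizes rest on an assumed mild share, assumed grade splits and a latent normal model, because the documents give no severity distribution. They also treat every clinician-mild event as unlogged, which ignores the hospital and emergency exception from 6 weeks to 6 months. The consequence is confined to a supplementary aim, but the correction is cheap enough that it should be made.

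**What to change.** In Appendix B sections 5.2 and 7, state that every Appendix B-3 item a patient reports receives a clinician grade on the standard AE log at any level, including mild. Keep the grade 2 floor for all other AEs. This removes the selection on clinician grade and brings the capture rule into line with section 8.1. The cost is a sentence in each section and a few more log entries for items that coordinators already ask about on the visit forms.

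If mild grades were not recorded, say so in the PPAR analysis plan. Label Aim 1 as agreement among events the clinician graded 2 or higher (plus the stated exceptions), do not present the lower/higher comparison as unbiased, and restate the kappa precision for the pairs actually available. That costs only wording and one recalculation.

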6. SELECTION OF PARTICIPANTS

Inclusion and Exclusion Criteria: All women who participate in ASPIRe will be included in this supplementary study, with the same inclusion and exclusion criteria. As with the primary ASPIRe study, only randomized and treated participants will be included in the analysis.

7. DESCRIPTION OF STUDY INTERVENTIONS

The PPAR AE Log form will be similar to the Standard AE Log Form used for the usual ranking process to capture the PPAR attributes (grade/severity at its worst, impact, frequency). The 6-week and 6-60 month postoperative ASPIRe visit forms will include the PPAR inventory items under "Subject Reported Complications Table" to streamline capture from the coordinator standpoint. PPAR items on these forms will be highlighted using a mechanism such as an *asterisk to alert the coordinator that additional PPAR forms will be required for those AEs/symptoms.

We will collect PPAR data at the time points outlined in Table 14.

Table 14. Collection of Patient-Perspective Information for AEs

Time point	Rationale
Initial identification of AE	Provides patient's initial perspective *This gets updated at each interaction such that the "most severe" reporting by the patient gets recorded.
12 months postop	Provides information about whether her perspective changed over time
3 years postop (or final visit)	Provides her final perspective about the AE at the primary endpoint of the ASPIRe trial

When a PPAR AE/symptom is identified, the research staff will capture the PPAR AE/symptom attributes with the patient. The research staff will complete the usual process as needed to complete the Standard AE Log Form as well as the PPAR AE log Form. The investigators will be masked to the patient reporting and the patients will be masked to the investigator reporting. The attributes will be captured in an ongoing fashion such that the highest severity reported by the participant will be recorded on the PPAR AE log. Her perspective will be reassessed at 12 months and 3 years postoperative. Whether or not (and when) the AE/symptom has resolved will be determined based on the Standard ASPIRe AE log form by the field "Event End Date".

We did consider capturing PPAR information at the time the AE/symptom resolves. The team decided that it would be challenging to collect the patient perspective at the exact time point that the participant considered the event or symptom resolved, as this would require fairly intense tracking. Therefore, tracking will not be performed to specifically define when an event or symptom resolved. However, again, an estimate of if and when the event/symptom resolved will be captured on the ASPIRe AE log form and will be used in PPAR analyses to determine whether the participant perspective was collected before or after resolution. If over time the AE worsens, then the PPAR attributes will be collected again to provide information regarding if her perspective has changed.

Logistically, the decision-making and quality of life scales are to be administered prior to obtaining PPAR information to minimize any bias that may occur with completing PPAR associated forms.

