4. STUDY OBJECTIVES AND PURPOSE OF PPAR

Aim 1: To compare patient vs. routine rankings* of AE/symptom grade.

This aim will provide information about the relevance and severity of adverse symptoms and events from the patient perspective via a ranking process and will also compare patient rankings with the routine ranking process.

We hypothesize that the patient ranking versus routine ranking processes will result in differences in perceived severity (grade) and impact.

* "Routine ranking" is defined as the usual PFDN process for grading AEs, which typically incorporates research staff and investigator/surgeon input.

Aim 2: To estimate the association between patient rankings of AE/symptom grade and impact to Decision Regret and Decision Satisfaction in ASPIRe.

We hypothesize that symptoms and events graded by patients as severe will be associated with higher Decision Regret and lower Decision Satisfaction scores compared to less severe events. This assessment will provide data to inform which events are associated with harm (negative impact on decision-making and quality of life outcomes).

Aim 3: To estimate the association between AEs/symptoms and quality of life and patient global impression outcomes (SF-12 and PGI-I).

We hypothesize that symptoms and events graded by patients as more severe will be associated with decreased quality of life and global impression scores. This also provides data to inform which events are associated with harm.

Aim 4: To determine if patient perspective about AEs/symptoms changes over time.

We hypothesize that the patient perspective about adverse symptom and events qualities such as grade and impact on decision-making and quality of life outcomes will change over time and ultimately plateau. This will potentially provide information about the most relevant time points at which to measure specific events.

Aim 5: To compare AE/symptom severity ranking between patient rankings and the Pelvic Floor Complication Scale.

[figure not shown]
We hypothesize that AE/symptom ranking based on patient perspective compared to the PFCS will be different. Because the PFCS was developed by the PFDN, it is important to provide validity data from the patient perspective.

Aim 6: To begin to develop a shared model of AE/symptom reporting, incorporating both patient and clinician input.

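### The PPAR record meant to hold a patient's initial view of an adverse event is updated to her most severe report, so Aim 4 comparisons that start from it hide worsening and lean toward decline when ratings vary

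*Protocol*

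**What the plan says.** Table 14 in Protocol Appendix B, section 7, lists three occasions for collecting the patient's view of an event: first identification, 12 months after surgery, and 3 years or the final visit. The reason given for the first is that it "Provides patient's initial perspective". A note in the same cell adds: "This gets updated at each interaction such that the 'most severe' reporting by the patient gets recorded".

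The text under the table repeats the rule. Attributes are captured on a running basis "such that the highest severity reported by the participant will be recorded on the PPAR AE log". It then treats the later occasions as distinct: "Her perspective will be reassessed at 12 months and 3 years postoperative". A further paragraph provides for worsening: "If over time the AE worsens, then the PPAR attributes will be collected again", the stated purpose being to learn whether her view has altered. There is no matching provision for an event that improves.

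The Aim 4 hypothesis (section 4) is that perspective "will change over time and ultimately plateau". The Aim 4 analysis (section 8.2) reads: "We will determine the intra-observer agreement for patient rankings of AE/symptom grade and impact over time using weighted Kappa measures". It names no pair of time points. In Table 13 (section 5.1) the severity descriptors refer to the worst level; the frequency and impact questions do not.

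**The concern.** One record has two jobs that cannot both be done. As a baseline for change it must hold the first rating. As a running maximum it must discard that rating whenever a higher one arrives. No section says that both are kept.

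Aim 4 needs the baseline. If the stored value is a maximum, two things follow for any comparison that starts from it. Worsening before the comparison visit is absorbed into the starting value and cannot be seen. And because the maximum of several ratings is set against a single later rating, ordinary variation between contacts pushes the difference downward. Change and plateau are what Aim 4 is meant to describe, so the storage rule could shape the answer.

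**Working it through.** **The plan's own figure.** None is given for Aim 4. The only PPAR precision figure is for Aim 1 (section 8.1): kappa 0.5 with half-width 0.11 at 400 events. With half-width = 1.96 x sqrt(po(1-po)/n)/(1-pe) and po = pe + 0.5(1-pe), n = 400 gives 0.063 at pe = 0.25, 0.085 at pe = 0.50 and 0.110 at pe = 0.67. The figure is attainable but cannot be confirmed without the grade distribution, and the present point does not depend on it.

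**Step 1: the rule applied by hand.** Code mild = 1, moderate = 2, severe = 3. No rating noise is assumed.

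| Ratings at first contact, a later contact, 12 months | Change from first rating | Change from stored maximum |
|---|---|---|
| 1, 3, 3 | +2 | 3 - 3 = 0 |
| 1, 3, 1 | 0 | 1 - 3 = -2 |

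The first row is genuine worsening that reads as no change. The second ends where it began but reads as a two-level fall.

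**Step 2: constant true severity with rating variability.** All inputs here are assumptions, since the documents give none: four ordered levels with true shares 0.30/0.40/0.25/0.05; each rating independently shifts one level, up or down equally, with probability q (truncated at the ends); contacts at 6 weeks and 6, 12, 18, 24, 30 and 36 months; 400,000 simulated events.

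For a maximum of two ratings fixed before 12 months there is a closed form. Since max(R1,R2) = (R1+R2)/2 + |R1-R2|/2, the expected change is -E|R1-R2|/2. For the two middle levels (share 0.65) E|R1-R2| = 2q - q^2; for the two end levels (share 0.35) it is half that. So mean change = -0.5 x (0.65 + 0.175) x (2q - q^2) = -0.4125(2q - q^2). At q = 0.2 this is -0.4125 x 0.36 = -0.149.

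| q | First rating kept: mean change; weighted kappa | Maximum fixed before 12 months, against 12 months: formula; simulated; lower/higher; kappa | Maximum through 36 months, against 36 months: mean change; lower/higher; kappa |
|---|---|---|---|
| 0 | 0.00; 1.00 | 0; 0; 0%/0%; 1.00 | 0; 0%/0%; 1.00 |
| 0.1 | 0.00; 0.84 | -0.078; -0.078; 11.9%/4.5%; 0.83 | -0.274; 26.6%/0%; 0.73 |
| 0.2 | 0.00; 0.70 | -0.149; -0.149; 22.0%/8.3%; 0.69 | -0.471; 44.1%/0%; 0.57 |
| 0.3 | 0.00; 0.59 | -0.210; -0.210; 30.0%/11.5%; 0.58 | -0.607; 54.7%/0%; 0.47 |
| 0.4 | 0.00; 0.49 | -0.264; -0.263; 36.1%/14.0%; 0.49 | -0.701; 60.5%/0%; 0.40 |

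If updating stops with the 12-month contact itself, then at q = 0.2 kappa against 12 months rises to 0.77 and no 12-month rating can be higher, while kappa against 36 months is 0.64. So even the direction of the distortion in kappa depends on when updating stops, which the text does not say.

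**Step 3: the contrast that avoids the record.** Comparing 12 months with 36 months gives mean change 0.00 and kappa 0.70 at q = 0.2, the same as with an unaltered first rating.

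**Step 4: true worsening, no noise.** With a one-grade rise after the first contact that persists, change to 36 months is +1.0 from the first rating and 0.0 from the running maximum.

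**The case against.** A good deal can be said for the plan.

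- The severity items refer to the worst level, so keeping the highest report matches what is being measured. This stands for severity as a measure of worst experience. It does not make that value a starting point for change, and Aim 4 also covers impact, for which no retention rule is given.
- Collecting the attributes again on worsening, in order to see whether her view has changed, implies an earlier value to compare with. The log form is not in the documents, and SAP section 3.2 leaves PPAR definitions and analyses to a separate SAP. So it is not shown that first ratings were lost. But the written rule replaces the value, and a later SAP cannot restore an entry that was never retained.
- Weighted kappa has no direction, and with the maximum fixed before 12 months it hardly changes. This stands.
- An event first identified at 6 months may have only one rating before 12 months, and a discrete event may be rated once. The share of events affected is unknown.

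A reader might infer that Aim 4 must show a decline even when nothing changes. The documents do not support that: identical ratings give zero change under every rule, a decline would appear only in a directional summary, and section 8.2 does not name the stored record as the comparator. Nor do they support extending the point to Aim 1, given the worst-level wording of the severity items, or to the real-time capture claimed in section 10. That claim contrasts with recall and hypothetical scenarios, and updating at each contact is still contemporaneous.

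**Conclusion.** The point holds in a limited form. By the written rule, the record labelled as the initial view is a running maximum. An Aim 4 comparison that begins from it cannot show worsening before the comparison visit; this follows from the rule alone. The lean toward decline also needs ratings to vary between contacts and more than one contact before the comparison.

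Over the assumed range q = 0.1 to 0.4, the downward shift is about 0.08 to 0.26 grade with the maximum fixed before 12 months, and kappa moves by no more than about 0.01. If updating runs through 3 years, the loss of agreement is clear (0.70 to 0.57 at q = 0.2) and no later rating can exceed the stored one. These sizes rest on assumed grade shares, independent noise and two to seven contacts per event.

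The matter is confined to one aim of a supplementary study and does not touch the trial's primary conclusions. It is worth correcting because the remedy is nearly free.

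**What to change.** In Appendix B, section 7 and Table 14, state that each rating of severity, impact and (for symptoms) frequency is stored as a separate dated entry and never overwritten. In section 8.2, name the first-identification entry as the Aim 4 baseline and list the pairs of time points to be compared. Derive the highest severity to date as a separate variable for analyses that need the worst level.

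For data already collected, the PPAR SAP should say whether original first entries can be recovered. If they cannot, base Aim 4 on the 12-month versus 3-year contrast and acknowledge that change during the first year cannot then be described.

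The cost is a few sentences and one date or sequence field on the PPAR log. The same questions are already asked, so patients carry no extra burden. No change to Aim 1 is needed.
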